# 9.4. Appendix 4: Study Phases and Treatment Emergent Adverse Events

Subjects who do not take study treatment who have will have events, log recordings and measurements assigned to pre-treatment.

Events, log recordings and measurements with missing dates will be assigned to ontreatment for subjects who have taken study treatment, unless there is evidence it was not on-treatment.

# 9.4.1. Study Phases for Measurements Taken at Visits (FEV1 and Vital Signs Only)

Study Phase	Definition
Pre-Treatment	Date ≤ Study Treatment Start Date
On-Treatment	Study Treatment Start Date < Date ≤ Study Treatment Stop Date + 1
Post-Treatment	Date > Study Treatment Stop Date + 1

These definitions would only apply to vital signs and FEV1 data, in which baseline measurements are taken on Day 1 pre-dose (as define in the Schedule of Activities). If the standard definition (Section 9.4.3) were used then the baseline data would be considered on-treatment as it occurs on Day 1 even though it occurs prior to first dose. As a result, a separate definition of study phase has been used to ensure this data to captured appropriately.

# 9.4.2. Study Phases for Bone Mineral Density Measurements Taken at Visits (Bone Mineral Density Data Only)

Study Phase	Definition
Pre-Treatment	Date ≤ Study Treatment Start Date
On-Treatment	Study Treatment Start Date < Date ≤ Study Treatment Stop Date + 30 days (1 month)
Post-Treatment	Date > Study Treatment Stop Date + 30 days

# 9.4.3. Study Phases for Adverse Events and All Other Data Recorded in Logs (excluding Concomitant Medications)

Study Phase	Definition
Pre-Treatment	Event Onset Date < Study Treatment Start Date
On-Treatment	Study Treatment Start Date ≤ Event Onset Date ≤ Study Treatment Stop Date + 1
Post-Treatment	Event Onset Date > Study Treatment Stop Date + 1

## 9.4.4. Study Phases for Concomitant Medications

Treatment phases for summaries of COPD and non-COPD concomitant medications will be defined as follows:

	Treatment Phase		
Definition	Pre-	On-	Post-
	Treatment	Treatment	Treatment
Subject did not take study treatment (e.g, screening failures) and conmed stop date > date of Screening or variable that asks if conmed is on-going (refer hereafter as goingmed) is "yes"	Y		
(Conmed start date <treatment "yes"="" (refer="" <="" <treatment="" and="" as="" asks="" conmed="" date="" date<="" hereafter="" if="" is="" medication="" of="" or="" prior="" priormed))="" screening="" start="" stop="" study="" taken="" td="" that="" to="" variable="">Y			</treatment>	Y		
(Conmed start date <treatment and="" date="" date<="" date≤conmed="" date≤treatment="" is="" or="" priormed="" start="" stop="" td="" treatment="" yes)="">Y	Y		</treatment>	Y	Y	
(Conmed start date <treatment (conmed="" and="" date="" is="" or="" priormed="" start="" stop="" yes)="">treatment stop date or goingmed is "yes")</treatment>	Y	Y	Υ
(Treatment start date≤conmed start date <treatment (treatment="" and="" date="conmed" date)="" date)<="" date≤conmed="" date≤treatment="" or="" start="" stop="" td="" treatment="">	Y		</treatment>		Y	
([Treatment start date≤conmed start date <treatment [treatment="" and(conmed="" date="" date]="" date])="" or="" start="" stop="">treatment stop date or goingmed is Yes)</treatment>		Y	Υ
Conmed start≥ treatment stop date and treatment start date ≠ treatment stop date			Υ

#### NOTES:

- A concomitant medication will be classed in every period of the study in which it was taken (e.g., run-in, ontreatment or post-treatment).
- See Section 9.7.2.1 for handling of partial dates.
- If the study treatment stop date is missing, it will be imputed as described in Section 9.6.2.
- Medications that stopped prior to Screening will not be assigned a treatment phase and will not be summarized.

# 9.4.5. Treatment Emergent Flag for Adverse Events, Pneumonia and Exacerbations

Flag	Definition
Treatment Emergent	
 
If AE onset date is on or after treatment start date & on or before treatment stop date plus one day.
 
Study Treatment Start Date ≤ AE Start Date ≤ Study Treatment Stop Date + 1.
 

#### NOTES:

- If the study treatment stop date is missing, then the AE will be considered to be On-Treatment.
- Time of study treatment dosing and start/stop time of AEs should be considered, if collected.

# 9.5. Appendix 5: Data Display Standards & Handling Conventions

## 9.5.1. Reporting Process

Reporting Process			
Software			
The currently supported versions of SAS software will be used.			
Reporting Area			
HARP Server	UK1SALX00175		
HARP Area	gw685698_gw642444\hzc102972\final_02		
QC Spreadsheet	gw685698_gw642444\hzc102972\final_02\documents		
Analysis Datasets			
Analysis datasets will be created according to CDISC standards			
Generation of RTF Files			
RTF files will be generated for all reporting efforts			

## 9.5.2. Reporting Standards

### **Reporting Standards**

#### General

- The current GSK Integrated Data Standards Library (IDSL) will be applied for reporting, unless otherwise stated:
  - 4.03 to 4.23: General Principles
  - 5.01 to 5.08: Principles Related to Data Listings
  - 6.01 to 6.11: Principles Related to Summary Tables
  - 7.01 to 7.13: Principles Related to Graphics

#### **Formats**

- All data will be reported according to the actual treatment the subject received unless otherwise stated.
- GSK IDSL Statistical Principles (5.03 & 6.06.3) for decimal places (DP's) will be adopted for reporting of data based on the raw data collected.
- Numeric data will be reported at the precision collected on the eCRF.
- The reported precision from non eCRF sources will follow the IDSL statistical principles but may be adjusted to a clinically interpretable number of DP's.

#### **Reporting Standards**

#### **Planned and Actual Time**

- Reporting for tables, figures and formal statistical analyses:
  - Planned time relative to dosing will be used in figures, summaries, statistical analyses and calculation of any derived parameters, unless otherwise stated.
  - The impact of any major deviation from the planned assessment times and/or scheduled visit days on the analyses and interpretation of the results will be assessed as appropriate.
- Reporting for Data Listings:
  - Planned and actual time relative to study drug dosing will be shown in listings (Refer to IDSL Statistical Principle 5.05.1).
  - Unscheduled or unplanned readings will be presented within the subject's listings.
  - Visits outside the protocol defined time-windows (i.e. recorded as protocol deviations) will be included in listings but omitted from figures, summaries and statistical analyses.

#### **Unscheduled Visits**

- Unscheduled visits will not be included in summary tables.
- Unscheduled visits will not be included in figures.
- All unscheduled visits will be included in listings.

#### **Descriptive Summary Statistics**

Continuous Data	Refer to IDSL Statistical Principle 6.06.1		
Categorical Data	N, n, frequency, %		
Reporting of Pharmacokinetic Concentration Data			
Descriptive	Refer to IDSL Statistical Principle 6.06.1		
Summary Statistics	Assign zero to NQ values (Refer to GUI_51487 for further details)		
Granhical Displays			

#### **Graphical Displays**

Refer to IDSL Statistical Principals 7.01 to 7.13.

## 9.6. Appendix 6: Derived and Transformed Data

#### 9.6.1. **General**

#### **Multiple Measurements at One Analysis Time Point**

#### **Bone Mineral Density Data:**

- If there are two values within a time window (as per Section 9.3.1) the mean of the measurements will be calculated and used in any derivation of summary statistics and for any analysis.
- If the data is listed however all data will be presented.

### **Study Day**

- Calculated as the number of days from First Dose Date:
  - Ref Date = Missing → Study Day = Missing
  - Ref Date < First Dose Date → Study Day = Ref Date First Dose Date

  - Ref Date ≥ First Dose Date → Study Day = Ref Date (First Dose Date) + 1

# 9.6.2. Study Population

#### Age

 Date of birth will be set as 30-JUN-YYYY where YYYY is the year of birth taken from the CRF. For subjects who attended a screening visit, age will be calculated at the screening visit date. For pre-screen failures, age will be calculated at the pre-screening visit date.

#### **Body Mass Index (BMI)**

BMI = Weight (kg) / Height(m)

#### **Study Treatment Stop Date**

If the treatment stop date is missing, it will be imputed as the minimum of:

- Date of death
- Study conclusion date
- Last dispensed date + number of doses dispensed and not returned

#### **Treatment Compliance**

• Treatment compliance will be calculated based on the formula:

#### Treatment Compliance = Number of Actual Doses / (Treatment Duration in Days \* Frequency)

- Frequency is once daily. Treatment compliance could be greater than 100% if there are events of overdose. Cumulative compliance (since Day 1) at each visit will be calculated.
- Compliance is based on number of doses taken across all containers dispensed and returned during the study – ie, it is calculated regardless of incorrect containers being dispensed. Any containers that are dispensed and not returned during the study are not included in the calculation. If any dose counter stop is missing, then the number of doses taken will be set to missing for that inhaler.
- Compliance will be summarized by the following categories:
  - <80%,
  - $\geq$  80% to < 95%,
  - ≥95% to <105%.
  - ≥ 105% to <120% and
  - ≥120%

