5. STUDY TREATMENTS

5.1. Investigational Product and Other Study Treatment

GSK Clinical Trials Supplies will provide the investigational products for use in this study. All blinded study medication will be delivered via the NDPI. At each dispensing each subject will receive NDPI for once-daily administration. The contents of each treatment are described in Table 1 and Table 2.

The NDPI provides a total of 30 doses (60 blisters), with each actuation comprising the contents of one blister from each of the two internal foil strips simultaneously. The NDPIs containing randomized treatment will appear identical on the outside to the subject (and his/her caregiver) and the Investigator.

All subjects will receive supplemental albuterol/salbutamol (MDI and/or nebules) to be used on an as-needed basis throughout the study; for all sites this medication will be sourced locally where possible.

Following the 14 to 21 day, Run-In period, eligible subjects will be randomized (1:1) to one of the following two possible treatments, administered each morning for 156 weeks:

- FF/VI Inhalation Powder 100/25mcg QD
- VI Inhalation Powder 25mcg QD

Randomization in each treatment group will be stratified (1:1) according to gender.

A description of the investigational treatments is provided below:

Table 1 Description of FF/VI Inhalation Powder Novel Dry Powder Inhaler (NDPI)

Formulation	First strip: Fluticasone Furoate blended with lactose	Second strip: Vilanterol micronised drug (as the 'M' salt triphenylacetate) blended with lactose and magnesium stearate ¹				
Dosage Form	Novel dry powder inhaler with 30 de	oses (2 strips with 30 blisters per strip)				
Unit Dose Strengths	100mcg per blister	25mcg per blister				
Physical description	Dry white powder	Dry white powder				
Route of Administration	Inhaled	Inhaled				

1. Magnesium stearate 1% w/w of total drug product

Table 2 Description of VI Inhalation Powder Novel Dry Powder Inhaler (NDPI)

Formulation	First strip: lactose	Second strip: Vilanterol micronised drug (as the 'M' salt triphenylacetate) blended with lactose and magnesium stearate ¹
Dosage Form	NDPI with 30 doses (2 strips	with 30 blisters per strip)
Unit Dose Strengths	N/A	25mcg per blister
Physical description	Dry white powder	Dry white powder
Route of Administration	Inhaled	Inhaled

1. Magnesium stearate 1% w/w of total drug product

CONFIDENTIAL

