#### **Extent of Exposure**

- Number of days of exposure to study drug will be calculated based on the formula:
  - Duration of Exposure in Years = (Treatment Stop Date (Treatment Start Date) + 1) / 365.25
- This will also be the exposure used to calculate rate of events
- Duration of exposure will be summarised by the following categories:
  - $\leq$  3months.
  - > 3 months < to  $\le$  6 months.
  - > 6 months to  $\leq$  12 months,
  - >12 months to  $\leq$  24 months.
  - >24 months to ≤ 36 months and
  - >36 months

where 1 month is equal to (365.25 days/12).

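### The compliance formula omits unreturned inhalers from doses taken without adjusting the days, so it understates compliance, mainly at early visits and after withdrawal

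*SAP*

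**What the plan says.** SAP Section 9.6.2 (Treatment Compliance) defines compliance as "Number of Actual Doses / (Treatment Duration in Days" multiplied by frequency), and adds "Frequency is once daily". The dose count is limited by source: "Compliance is based on number of doses taken across all containers dispensed and returned during the study". Unreturned inhalers are then ruled out: "Any containers that are dispensed and not returned during the study are not included in the calculation". For a returned inhaler whose counter cannot be read, "If any dose counter stop is missing, then the number of doses taken will be set to missing for that inhaler". The timing is also set: "Cumulative compliance (since Day 1) at each visit will be calculated".

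Treatment duration is not defined in that item. The nearest definition is the adjacent Extent of Exposure item, which uses plain calendar time from treatment start to stop.

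In the same section, a missing treatment stop date is imputed as the earliest of three dates: death, study conclusion, and the last dispensing date plus the doses given out but not brought back.

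Results go into five percentage bands, the lowest being under 80%. The planned displays are Table 1.31 and Listing 27.

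**The concern.** An inhaler that does not come back carries unknown information: its doses may or may not have been taken. The formula takes those doses out of the numerator but has no term that takes the matching days out of the denominator. Unknown use is therefore scored as no use, and the error can only go downward.

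Compliance is one of the few planned displays of doses actually taken. SAP Section 9.1.1 rules out a per-protocol population, Section 7.1.4 keeps BMD data after temporary discontinuation, and the exposure summary measures calendar time. A reader of a non-inferiority result will look at Table 1.31 to judge whether the fluticasone furoate contrast was maintained.

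**Working it through.** The documents state no compliance result, so there is no figure to reproduce.

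**Inputs**
- Doses per inhaler: 30 (Protocol Section 5.1: "The NDPI provides a total of 30 doses (60 blisters").
- Frequency: 1 per day (SAP Section 9.6.2).
- Full treatment period: 156 × 7 = 1,092 days, as SAP Section 9.6.3 also states.
- Visits every 13 weeks = 91 days (Protocol Table 3).
- Assumptions: treatment duration is calendar days; each lost inhaler was fully used (fewer doses means a smaller bias); the subject took every dose.

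**Formula.** With k unreturned inhalers over T days, reported compliance = (T − 30k)/T. True compliance is 100%.

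**Cumulative values by visit**

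| Time point | T (days) | k = 1 | k = 2 |
|---|---|---|---|
| Week 13 | 91 | 61/91 = 67.0% | 31/91 = 34.1% |
| Week 26 | 182 | 152/182 = 83.5% | 122/182 = 67.0% |
| Week 52 | 364 | 334/364 = 91.8% | 304/364 = 83.5% |
| Week 156 | 1,092 | 1,062/1,092 = 97.3% | 1,032/1,092 = 94.5% |

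Across the ±14-day visit window, the Week 13 value with k = 1 runs from 47/77 = 61.0% to 75/105 = 71.4%.

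**Thresholds.** One lost inhaler gives a value under 80% only if 30/T > 0.20, that is T < 150 days. It gives a value under 95% only if 30/T > 0.05, that is T < 600 days. Over 1,092 days, seven lost inhalers give 882/1,092 = 80.8% and eight give 852/1,092 = 78.0%.

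**Withdrawal with a missing stop date.** Assume four inhalers (120 doses) dispensed at Day 91, none returned, perfect use until the subject stops, neither death nor study conclusion earlier than the imputed date, and the imputed date used for treatment duration. The stop date becomes Day 91 + 120 = Day 211. The numerator holds only the 91 doses from returned inhalers, so reported compliance = 91/211 = 43.1%, wherever between Day 91 and Day 211 the subject really stopped. The stop-date rule counts the unreturned doses as time on treatment, while the compliance rule leaves them out.

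**Two possible corrections.** Suppose a fully adherent subject returns three used inhalers (90 doses) in a 91-day interval and loses a fourth after one dose.
- As written: 90/91 = 98.9%, close to the truth.
- Deducting a flat 30 days: 90/(91 − 30) = 90/61 = 148%, in the top band.
- Removing the whole interval from both parts leaves only the other intervals. At Week 156 that is (1,092 − 91)/(1,092 − 91) = 100%.

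**The case against.** The strongest reply is that the SAP excludes unreturned inhalers from the calculation, not from the numerator alone, and that treatment duration is undefined here. On that reading the text is ambiguous rather than wrong. This stands in part: that the days stay in the denominator is inferred from the formula and the absence of any adjustment. But the formula has no container-level term through which a programmer could remove them, so clarification is needed on either reading.

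A reader might infer that any fully adherent subject who loses an inhaler is reported as non-compliant. The documents do not support that. A completer with one loss stays in the 95% to under 105% band, and the SAP uses bands, with no non-compliant label. The protocol's 80% to 120% range (Sections 4.4 and 5.5) applies between consecutive visits and not to the cumulative figure.

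Nor does the text say that an unreadable counter is scored as zero. Its doses become missing for that inhaler; whether the subject's total then becomes missing or skips it is not stated.

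It is also fair that Listing 27 is titled as overall compliance and that the table shells are not included, so early-visit values may not be tabulated. Exposure, the Kaplan-Meier plot of discontinuation, protocol deviations and misallocations also bear on whether the contrast was maintained. Understated compliance makes a non-inferiority conclusion look less secure, not more. A difference in bias between arms is possible if returns or withdrawals differ, but nothing in the documents shows that they would, and the inhalers look identical under a double blind.

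**Conclusion.** The mechanism holds on the text as written. The dose count loses unreturned inhalers, no rule adjusts the days, and compliance is biased down by up to 30/T per inhaler. The bias is minor for completers (2.7 points per inhaler). It is material for cumulative values at the first visits, for treatment shorter than 150 days, and for withdrawals without returns, where the stop-date imputation can add to it. These sizes assume fully used lost inhalers and calendar-day duration.

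The consequence is confined to Table 1.31 and Listing 27. Compliance is not a term in the BMD model (SAP Section 7.1.5.1) and defines no analysis population (Section 4), so the non-inferiority result does not change. This is a low-severity point worth correcting because the bias runs one way and the correction is cheap.

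**What to change.** In SAP Section 9.6.2:

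1. Define treatment duration for compliance, both overall and for the cumulative figure at each visit.
2. For any dispensing interval with an unreturned inhaler or an unreadable counter, remove the interval from both parts of the ratio: all its doses and all its days. Do not deduct a flat 30 days per inhaler, which can overshoot as shown. If no interval remains, set compliance to missing.
3. Reconcile this with the stop-date imputation, so that unreturned doses do not lengthen the denominator while being left out of the numerator.
4. Report by arm the number of subjects and intervals affected.

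The cost is a short addition to the derivation and some reprogramming, with no new data. The downside is that removed intervals give no compliance information, including at Week 13 when the first interval is affected, and their use is assumed to resemble that in the observed intervals. The counts by arm let the reader judge how far that assumption matters.

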#### **Extent of Exposure**

- Number of days of exposure to study drug will be calculated based on the formula:
  - Duration of Exposure in Years = (Treatment Stop Date (Treatment Start Date) + 1) / 365.25
- This will also be the exposure used to calculate rate of events
- Duration of exposure will be summarised by the following categories:
  - $\leq$  3months.
  - > 3 months < to  $\le$  6 months.
  - > 6 months to  $\leq$  12 months,
  - >12 months to  $\leq$  24 months.
  - >24 months to ≤ 36 months and
  - >36 months

where 1 month is equal to (365.25 days/12).

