Dispense Single-Blind Medication		Х															
Dispense Double- Blind Medication			Х	Х	Х	Х	Х	Х	Х	Х	Х	Х	Х	Х			
Collect Blinded Medication			Х	Х	Х	Х	Х	Х	Х	Х	Х	Х	Х	Х	Х	Х	
Other Assessment																	

2012N150072_01

CONFIDENTIAL

2018N368712_00 HZC102972

Double-Blind Treatment period 2 3 15 0 1 4 5 6 7 8 9 10 11 12 13 14 Random-Pre-Screen-Early Follow Visit Number screen1 ing² ization With--up draw 13 26 39 52 65 78 91 104 117 130 143 156 Visit Day 1 wks 14/EW ± 14 ± 14 ±14 ± 14 ± 14 ± 14 ±14 + 7±2 ± 14 ± 14 ± 14 ± 14 ± 14 Days Days Days Davs Days Days Days Davs Days Days Days Days Days Discharge from Х Х Study¹⁵

1. Visit 0 and Visit 1 may occur on the same day if the subject does not take or has not taken any protocol excluded medications.

- 2. Following Screening Visit 1, subjects enter a 14 to 21 day single-blind run-in period.
- 3. Subjects will be assigned a subject number at the time ICF is signed. The ICF must be signed before any study procedures including medication exclusion period(s).
- 4. Saliva (2ml) sample is collected in the DNA self-collection kit. This should ideally be taken as soon after randomization (Visit 2) as possible, but may be taken at any other visit after randomization if necessary. PGx consent must be signed prior to PGx sampling.
- 5. A telephone based IVRS system (RAMOS) which will be used by the investigator or designate to register the subject, randomize the subject and provide medication assignment information.
- 6. Baseline BMD measurements will be collected between Visit 1 and Visit 2.
- 7. If evidence of infection, culture swab may be taken and appropriate therapy should be instituted at Investigator discretion. Subjects with culture-positive infection may continue in the study on appropriate anti-infective treatment at Investigator discretion.
- 8. Chest X-ray must be taken if a Chest X-ray or CT scan is not available within the 12 months preceding Visit 1. Chest x-rays will be requested for suspected cases of pneumonia.
- 9. Non-fasting and pre-dose. A blood sample for repeat analysis is collected only if any part of Screening lab needs to be repeated. Results of repeat labs should be received prior to Randomization at Visit 2.
- 10. Females of child-bearing potential only
- 11. Adverse events are to be collected from the start of blinded study medication (Visit 2) until the follow-up phone contact.

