#### Rate of Adverse Events per 100 Treatment Years

Rate of on-treatment adverse events per 100 treatment years will be calculated using:

Rate = number of events \* 100 / total treatment exposure in years

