2.18.	SAF	SAFE_T04	Analysis of On-treatment Percentage Change from Baseline in Bone Mineral Density (g/cm^2) at the Lumbar Spine by Gender		SAC [1]	
2.19.	SAF	SAFE_T05	On-treatment Bone Mineral Density (g/cm^2) at the Lumbar Spine Mixed Model Repeated Measures Analysis Interaction Test	Only include the interaction for gender	SAC [1]	

Safety:	Tables				
No.	Population	IDSL / Example Shell	Title	Programming Notes	Deliverable [Priority]
Vital Si	gns, Incidence	of Fracture, Pneu	monia, X-rays and COPD Exacerbations		
2.20.	SAF	VS1	Summary of Vital Signs	All variables to have a row for minimum and maximum ontreatment values along with having a row for early withdrawal.	SAC [1]
2.21.	SAF	VS1	Summary of Change from Baseline in Vital Signs	All variables to have a row for minimum and maximum ontreatment values along with having a row for early withdrawal.	SAC [1]
2.22.	SAF	SAFE_T07	Summary of On-treatment Pneumonia		SAC [1]
2.23.	SAF	SAFE_T08	Summary of On-treatment Fractures		SAC [1]
2.24.	SAF	SAFE_T09	Summary of On-treatment Moderate/Severe COPD Exacerbations		SAC [1]
2.25.	SAF	SAFE_T09	Summary of On-treatment Severe COPD Exacerbations		SAC [1]
Spiron	netry				
2.26.	SAF	SAFE_T10	Summary of On-treatment FEV 1 (L) at Clinic Visits		SAC [1]
2.27.	SAF	SAFE_T10	Summary of On-treatment FVC (L) at Clinic Visits		SAC [1]
Advers	e Events			·	
2.28.	SAF		Overview of On-treatment Adverse Events During the Study		SAC [1]
2.29.	SAF	AE1	Summary of On-treatment Adverse Events Leading to Permanent Discontinuation of Study Treatment or Withdrawal from the Study by System Organ Class and Preferred Term	IDSL - Include rates.	SAC [1]

Safety:	Safety: Tables					
No.	Population	IDSL / Example Shell	Title	Programming Notes	Deliverable [Priority]	
2.30.	SAF	AE1	Summary of On-treatment Adverse Events by System Organ Class and Preferred Term	ICH E3. Include rates.	SAC [1]	
2.31.	SAF	AE1	Summary of On-treatment Adverse Events by Age	IDSL. Use age ranges: 40 to ≤ 65, >65 to ≤ 74, and ≥75	SAC [1]	
2.32.	SAF	AE1	Summary of On-treatment Adverse Events by Region	IDSL, North America vs Europe	SAC [1]	
2.33.	SAF	AE1	Summary of On-treatment Adverse Events by Gender	IDSL	SAC [1]	
2.34.	SAF	AE1	Summary of On-treatment Adverse Events by Smoking Status	IDSL	SAC [1]	
2.35.	SAF	AE1	Summary of Post-treatment Adverse Events by System Organ Class and Preferred Term	ICH E3. Include rates.	SAC [1]	

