2.36.	SAF	AE1	Summary of On-treatment Drug-related Adverse Events by System Organ Class and Preferred Term	Include rates.	SAC [1]	
2.37.	SAF	AE1	Summary of On-treatment Drug Related Adverse Events	Number and % of subjects	SAC [1]	
2.38.	SAF	AE1	Summary of On-treatment Drug Related Serious Adverse Events	Number and % of subjects	SAC [1]	
2.39.	SAF	AE3	Summary of Common (>=3%) On-treatment Adverse Events by Overall Frequency	ICH E3	SAC [1]	
2.40.	SAF	AE15	Summary of Common (>=3%) Non-serious Adverse Events by System Organ Class and Preferred Term (Number of Subjects and Occurrences)	FDAAA, EudraCT	SAC [1]	
Seriou	s Adverse Even	nts				
2.41.	SAF	AE1	Summary of On-treatment Serious Adverse Events by System Organ Class and Preferred Term		SAC [1]	
2.42.	SAF	AE16	Summary of Serious Adverse Events by System Organ Class and Preferred Term (Number of Subjects and Occurrences)	FDAAA, EudraCT. Include rates.	SAC [1]	

Safety:	Tables						
No.	Population	IDSL / Example Shell	Title	Programming Notes	Deliverable [Priority]		
2.43.	SAF	AE1	Summary of On-treatment Serious Adverse Events Leading to Permanent Discontinuation of Study Treatment by System Organ Class and Preferred Term	IDSL	SAC [1]		
2.44.	SAF	AE16	Summary of On-treatment Fatal Serious Adverse Events by System Organ Class and Preferred Term		SAC [1]		
2.45.	SAF	AE16	Summary of On-treatment Non-fatal Serious Adverse Events by System Organ Class and Preferred Term		SAC [1]		
2.46.	SAF	AE16	Summary of On-treatment Drug-related Serious Adverse Events by System Organ Class and Preferred Term		SAC [1]		
Advers	Adverse Events of Special Interest						
2.47.	SAF	AE1	Summary of On-treatment Adverse Events of Special Interest	Include rates.	SAC [1]		
2.48.	SAF	AE1	Summary of On-treatment Serious Adverse Events of Special Interest	Include rates.	SAC [1]		

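### SAP Table 2.35 asks for rates of post-treatment adverse events, but the only exposure defined for rates is on-treatment time; applied literally, the rates come out about two orders of magnitude too low.

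*SAP*

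**What the plan says.** Table 2.35 in SAP 9.9.6 is titled "Summary of Post-treatment Adverse Events by System Organ Class and Preferred Term". Its programming note reads "ICH E3. Include rates", the same note that Table 2.30, the main on-treatment adverse event table, carries.

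SAP 9.6.2 (Extent of Exposure) computes exposure as treatment stop date minus start date plus 1, over 365.25, and adds: "This will also be the exposure used to calculate rate of events". SAP 9.6.3 gives one rate, introduced by "Rate of on-treatment adverse events per 100 treatment years will be calculated using" and defined as "Rate = number of events \* 100 / total treatment exposure in years". Neither section defines person-time after treatment.

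SAP 9.4.3 places an adverse event in the post-treatment phase when "Event Onset Date > Study Treatment Stop Date + 1". Collection ends at the follow-up call. Footnote 11 to Protocol Table 3 says: "Adverse events are to be collected from the start of blinded study medication (Visit 2) until the follow-up phone contact". Table 3 sets that call at 7±2 days after Visit 14 or early withdrawal; Protocol 3.1 sets it 7 days after the last treatment day.

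Table 2.42 is titled "Summary of Serious Adverse Events by System Organ Class and Preferred Term (Number of Subjects and Occurrences"), is also marked for rates, and unlike Table 2.41 is not limited to on-treatment events.

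**The concern.** A rate needs events and person-time from the same period. In Table 2.35 the events can arise only after the stop date plus one day, while the defined exposure ends on the stop date. The denominator contains none of the time in which a counted event could start, and it is far longer than that time.

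The study's purpose is safety, and adverse events are listed among its endpoints. Table 2.35 is the planned summary of events after stopping. Read beside Table 2.30, its rate column would suggest that events almost vanish once treatment ends, purely because of the denominator. In addition, if the arms differ in time on treatment, the post-treatment rates would differ for a reason unrelated to post-treatment risk.

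**Working it through.** **Inputs**
- Planned treatment: 156 weeks = 156 × 7 = 1092 days (the SAP's own figure, in the censoring rule for the Kaplan-Meier plot, 9.6.3).
- Run-in: 14 to 21 days. Follow-up call: nominally 7 days after treatment, ±2 in Protocol Table 3.
- Post-treatment phase: starts on stop date + 2 (SAP 9.4.3).
- Planned completion: 224 of 280 = 80% (Protocol 4.1).

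**Check on the nominal follow-up.** The Protocol Summary gives total participation as about 159 to 160 weeks. (14 + 1092 + 7)/7 = 159.0 and (21 + 1092 + 7)/7 = 160.0. The stated figure reproduces, so the nominal follow-up of one week is right.

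**Post-treatment window.** If the last dose falls on the day of Visit 14 or early withdrawal, the window runs from stop + 2 to stop + 7, which is 6 days. With the call at stop + 5 or stop + 9 it is 4 or 8 days.

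**Understatement factor** = mean on-treatment days / mean post-treatment days.

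| Mean exposure | 6 days | 8 days | 4 days |
|---|---|---|---|
| Completer, 1092 days | 182 | 136.5 | 273 |
| 80% complete, 20% leave evenly over time: 0.8 × 1092 + 0.2 × 546 = 983 days | 164 | 123 | 246 |
| 80% complete, 20% contribute no exposure: 0.8 × 1092 = 874 days | 146 | 109 | 218 |

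The two 80% rows are assumptions about when subjects leave. The protocol gives only the completion target.

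**Illustration** (assumed: 10 post-treatment events in an arm of 140, all completers)
- Literal SAP denominator: 140 × 1092/365.25 = 418.6 years; 10 × 100/418.6 = 2.4 per 100 years.
- Time at risk: 140 × 6/365.25 = 2.30 years; 10 × 100/2.30 = 435 per 100 years (326 at 8 days, 652 at 4 days).

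**Sensitivity to time in study off drug** (assumed fractions and durations)
- 5% of subjects staying 180 days: mean window 6 + 0.05 × 180 = 15 days; 983/15 to 1092/15 = about 66 to 73.
- 10% staying 180 days: mean window 6 + 0.10 × 180 = 24 days; 983/24 to 1092/24 = about 41 to 46.

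**Table 2.42.** At a constant event rate, 6 further days beside 1092 would add 6/1092, or about 0.5%, to the numerator. Serious events before treatment enter only if related to study participation or to a sponsor's concomitant medication (Protocol 6.2.13).

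**The case against.** The strongest reply is that the formula in SAP 9.6.3 covers on-treatment events only, so the SAP never tells the programmer to apply it to Table 2.35. That is correct, and it rules out saying that the SAP's formula prescribes the wrong rate for that table. It does not rescue the table. A rate is still requested, and the only guidance left is the general statement in 9.6.2, which points to treatment exposure. The post-treatment rate is thus either undefined or mis-defined, and both need correcting.

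The size can also be challenged. The 6-day window assumes that the last dose coincides with Visit 14 or early withdrawal, whereas Table 3 ties the call to the visit. The documents do allow time in study off drug:
- Under Protocol 6.2.7, subjects who meet a liver stopping criterion come off drug at once and leave the study after monitoring.
- Under Protocol 4.4, early discontinuation of drug leads to a discussion of continued participation.
- SAP 7.1.4 makes provision for BMD data collected after permanent discontinuation.

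This stands: no figure in the table above is a bound, and the factor could be well below 100.

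The harm has limits too. Protocol 8.3.5.2.2 requires numbers and percentages of subjects, with post-treatment events summarised separately, and SAP Listings 11 and 14 show every adverse event and serious adverse event. A reader might infer that a cluster of events after stopping would be hidden. It would be masked in the rate column only. Nor is a between-arm comparison distorted 182-fold: the same scaling applies to both arms, so the rate ratio shifts only as far as the arms differ in exposure or in post-treatment follow-up. The mock shells are not in the document, so how Tables 2.30 and 2.35 label their rate columns cannot be checked.

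**Conclusion.** The defect holds for Table 2.35: a rate is requested for which the SAP defines no suitable person-time, and its one general statement on exposure leads to the wrong denominator. Followed literally, it makes the post-treatment rate too low by about two orders of magnitude: 182-fold for a completer (about 137 to 273), and about 109 to 246 across the two 80%-completion scenarios. These figures rest on the last dose being at Visit 14 or early withdrawal and on no further time in study off drug. With 5% to 10% of subjects staying 180 days off drug, the factor would be roughly 41 to 73, still a gross error.

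A reader might be tempted to set a firm range of about 90 to 270. The documents do not support it. A value near 90 needs a mean exposure of about 2 years with an 8-day window (730.5/8 = 91). No such exposure is stated, and the 80%-completion and full-exposure cases give 2.39 to 2.99 years. Off-drug time could take the factor lower still.

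The consequence is confined to a descriptive rate column. It is worth correcting because the number would be wrong and the repair is almost free. Table 2.42 is a minor matter of scope with a probably small numerical effect, and should not be read as an error of the same order.

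**What to change.** **Preferred:** delete the rate request from the programming note of Table 2.35 and show n and % only. Total post-treatment person-time would be about 280 × 6/365.25 = 4.6 years, so a single event would move the pooled rate by about 100/4.6 = 22 per 100 years. Such a rate would be too unstable to be useful.

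**Alternative:** add to SAP 9.6.3 a post-treatment rate whose denominator is the sum over subjects of max(0, date of last study contact or death − (treatment stop date + 1)) / 365.25, and limit the general exposure statement in 9.6.2 to on-treatment rates. The floor at zero is needed because SAP 9.6.2 can impute a missing stop date as the date of death, which would otherwise give negative time.

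**Minor:** in Table 2.42, limit the rate to on-treatment serious events, or drop it and keep subjects and occurrences.

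**Cost:** SAP wording and at most one derived variable; no new data.
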